9.4.2. Assessment of Severity

The severity, or intensity, of an AE refers to the extent to which an AE affects the participant's daily activities or their health. The intensity of the AE will be rated in accordance with the CTCAE Version 5.0. Adverse events related to temperature and abnormal laboratory results that are not found in the CTCAE Version 5.0 will be rated in accordance with the FDA Guidance for Industry *Toxicity Grading Scale for Healthy Adult and Adolescent Volunteers Enrolled in Preventive Vaccine Clinical Trials* [Appendix [14.4 Toxicity Grading Scale](#)].

Changes in the severity of an AE should be documented to allow an assessment of the duration of the event at each level of intensity to be performed. Adverse events characterized as intermittent do not require documentation of onset and duration of each episode.

9.4.3. Assessment of Causality

The investigator's assessment of an AE's relationship to IMP is part of the documentation process. Regardless of the investigator's assessment of an AE's relationship to IMP, the AE must be reported.

The relationship or association of the IMP in causing or contributing to the AE will be characterized using the following classification and criteria:

Unrelated: There is no association between the IMP and the reported events.

Possible: Treatment with the IMP may have caused or contributed to the AE, i.e., the event follows a reasonable temporal sequence from the time of drug administration or follows a known response pattern to the IMP but could also have been produced by another factor.

Probable: A reasonable temporal sequence of the event with drug administration exists and based upon the known pharmacological action of the drug, known or previously reported adverse reactions to the drug or class of drugs, or judgment based on the investigator's clinical experience, the association of the event with the IMP seems likely. The event disappears or decreases on cessation or reduction of the dose of IMP.

Definite: A definite causal relationship exists between drug administration and the AE, and other conditions (concurrent illness, progression/expression of disease state, or concurrent medication reaction) do not appear to explain the event. The event reappears or worsens if the IMP is re-administered.

9.4.4. Description of Adverse Events

When recording an AE, the Investigator should use the overall diagnosis or syndrome using standard medical terminology, rather than recording individual symptoms or signs. The eCRF and source documents should be consistent. Any discrepancies between the participant's own words on his/her own records (e.g., diary card) and the corresponding medical terminology should be clarified in the source documentation.

Details for completion of the Adverse Event eCRF are described in the eCRF Completion Guidelines.

9.5. Reporting Serious Adverse Events

Serious Adverse Events (SAEs) must be reported to the Medical Monitor and Sponsor immediately, without undue delay but no later than within 24 hours of the site learning of the SAE.

To report the SAE, the investigator must record the SAE on the AE eCRF in the EDC system as well as any relevant CRF forms (e.g., drug dispensation CRF, applicable laboratory CRF). When the AE CRF is completed, [REDACTED] Safety personnel will be automatically notified electronically and will retrieve the form.

If the event meets serious criteria and it is not possible to access the EDC system, the back-up paper SAE Form must be completed in English with as much information that is known at the time and emailed to [REDACTED]. If email is unavailable the SAE can be reported via the [REDACTED] SAE hotline, and a copy of the completed paper SAE Form faxed to [REDACTED] within 24 hours of awareness. When the EDC system becomes available, the SAE information must be entered within 24 hours of the system becoming available.

The Sponsor has the legal responsibility to notify both the local regulatory authority and other regulatory agencies about the safety of an IMP under clinical investigation. The Sponsor will comply with country-specific regulatory requirements relating to safety reporting to the regulatory authority, IRB/IEC, and Investigators.

An Investigator who receives a safety notification letter describing a SUSAR or other specific safety information from the Sponsor, will review and will notify the local IRB/IEC, if appropriate according to local requirements.

9.5.5. Follow Up of Adverse Events

All AEs must be followed to satisfactory resolution, until the Investigator deems the event to be chronic or not clinically significant, the event is considered stable, the participant dies, or the participant is lost to follow-up. However, any new AEs that start more than 28 days after the final dose and changes in AEs that occur after the participant's end of study visit will not be recorded in the eCRF.

9.6. Pregnancy

Pregnancy is not regarded as an AE unless there is a suspicion that an IMP may have interfered with the effectiveness of a contraceptive medication. Any pregnancy that occurs during study participation or up to 28 days after the final dose of IMP must be reported to [REDACTED] Clinical Safety by phone or email, within 2 weeks of learning of its occurrence. [REDACTED] Clinical Safety will send the Exposure in Utero Form to the site for completion within 24 hours. This form should be completed and returned to [REDACTED] Clinical Safety within 24 hours of receipt.

All SAEs occurring in association with a pregnancy, brought to the Investigator's attention after the participant has completed the study must be promptly reported to [REDACTED] Clinical Safety.

Please see [Appendix 14.2 Contraceptive Guidance and Collection of Pregnancy Information](#) for further information.

9.7. Overdose

Excessive dosing (greater than a total of four ((4)) capsules within 24 hours) should be recorded in the CRF. Participants will be instructed to contact the Investigator or study coordinator immediately in the event of a suspected overdose.

Any confirmed overdose must be promptly reported to [REDACTED] Clinical Safety via the Special Situations Form. Overdose itself is not to be reported as an AE; however, any AEs or SAEs associated with the overdose are to be reported on relevant AE/SAE sections in the eCRF and on

the Paper SAE Form provided to [REDACTED] Clinical Safety (**Section 9.5 Reporting Serious Adverse Events**).

In the event of a symptomatic overdose, the Investigator should:

1. Manage the participant symptomatically with supportive care
2. Contact the Medical Monitor urgently
3. Document the quantity of the excess dose in the eCRF
4. Document the overdose symptoms and their duration in the eCRF

Doses of EDP1815 capsules that have previously been administered in participants with atopic dermatitis include a dose of 8.0×10^{11} cells taken once daily for 16 weeks, and 1.28×10^{12} cells taken once daily for 8 weeks. There are no specific adverse events expected in an overdose; however, the participant should be closely and carefully monitored. There is no specific treatment or antidote, but supportive clinical care should be provided as dictated by the participant's clinical status.

Decisions regarding dose interruptions or modifications will be made by the Investigator in consultation with the Medical Monitor based on the clinical evaluation of the participant.

9.8. Safety Signal Detection

Selected data from this study will be reviewed periodically to detect as early as possible any safety concern(s) related to the IMP so that Investigators, participants, regulatory authorities, and IRBs/IECs will be informed appropriately and as early as possible.

The Medical Monitor or medically qualified designee/equivalent will conduct an ongoing review of SAEs. [REDACTED] DM will perform ongoing SAE reconciliations in collaboration with the PV representative.

As appropriate for the stage of development and accumulated experience with the IMP, medically qualified personnel at the Sponsor may identify additional safety measures (e.g., AEs, vital signs, laboratory, or ECG results) for which data will be periodically reviewed during the course of the study.

9.9. Study Halting Criteria

The study will be halted if any of the following occur:

- One or more SAE considered definitely or probably related to the investigational product.
- Three or more participants with grade 3 AEs of the same type considered definitely, probably, or possibly related to the investigational product.
- Any participant develops a documented *Prevotella histicola* infection in a sterile space confirmed by clinical culture and/or qPCR.

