3. STUDY VARIABLES

3.1. Safety Variable(s)

3.1.1. Primary Safety Variable(s)

The primary safety variables will be the incidence and rate per 100 patient-years of TEAEs. Both the period defined by this study alone and the period defined by this study and the relevant parent study will be reported.

Subgroups of TEAEs will be evaluated as follows:

- All TEAEs
- TEAEs of Grade 2 or above
- TEAEs of Grade 3 or above
- Serious TEAEs
- Fatal TEAEs
- TEAEs causing discontinuation of study drug

- Study drug related TEAEs Study (defined by an investigator assessment of possible, probable, or definite relationship to IMP)
- Study drug related TEAEs of Grade 2 or above
- Study drug related TEAEs of Grade 3 or above
- Study drug related serious TEAEs
- Study drug related fatal TEAEs
- Study drug related TEAEs causing discontinuation of study drug

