9.3. Serious Adverse Events

A serious adverse event (SAE) is defined as an adverse event that meets any of the following criteria:

- Results in death.
- Is life-threatening that is, poses an immediate risk of death as the event occurred.
 - This serious criterion applies even if the participant, in the view of the Investigator or Sponsor, is at immediate risk of death from the AE as it occurs. It does not apply if an AE hypothetically might have caused death if it were more severe.
- Requires inpatient hospitalization or prolongation of existing hospitalization.
 - A participant admitted to a hospital, even if he/she is released on the same day, meets the criteria for the initial inpatient hospitalization. An emergency room visit that results in admission to the hospital would also qualify for the initial inpatient hospitalization criteria. However, emergency room visits that do not result in admission to the hospital would not

- qualify for this criterion and, instead, should be evaluated for one of the other criteria in the definition of serious (e.g., life-threatening adverse experience, important medical event).
- Hospitalizations for reasons not associated with the occurrence of an AE (e.g., preplanned surgery or elective surgery for a pre-existing condition that has not worsened or manifested in an unusual or uncharacteristic manner) do not qualify for reporting.
 - For example, if a participant has a condition recorded on his/her medical history and later has a preplanned surgery for this condition, it is not appropriate to record the surgery or hospitalization as an SAE, since there is no AE upon which to assess the serious criteria.
 - Please note that, if the pre-existing condition has worsened or manifested in an unusual or uncharacteristic manner, this would then qualify as an AE and, if necessary, the seriousness of the event would need to be determined.
 - Results in persistent or significant disability or incapacity.
 - This serious criterion applies if the “disability” caused by the reported AE results in a substantial disruption of the participant’s ability to carry out normal life functions.
 - Results in a congenital anomaly or birth defect in the offspring of the participant (whether the participant is male or female).

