 - Is an important medical event that, based upon appropriate medical judgment, may jeopardize the participant, and may require medical or surgical intervention to prevent one of the other outcomes listed in the definition of serious.
 - Examples of such medical events include allergic bronchospasm requiring intensive treatment in an emergency room or at home, blood dyscrasias that do not result in inpatient hospitalization, or the development of drug dependency or drug abuse.

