9.4. Reporting and Recording AEs

The Investigator will carefully monitor each participant throughout the study for possible AEs. In order to confirm complete safety data collection, all AEs occurring during the study (i.e., after the signing of the Informed Consent form) must be reported in the CRF. AEs reported during the parent study that are ongoing at the end of treatment visit will continue to be followed up during EDP1815-208 until resolution or the participants completes the study, whichever is first.

All AEs will be collected and reported in the electronic data capture (EDC) system and compiled into reports for periodic reviewing by the Medical Monitor. The Medical Monitor shall promptly review all information relevant to the safety of the investigational product, including all serious adverse events (SAEs). Special attention will be paid to those that result in permanent discontinuation of the investigational product being studied, whether serious or non-serious.

If the investigator learns of any SAE, including a death, at any time after a participant has been discharged from the study, and he/she considers the event to be reasonably related to the IMP or study participation, the investigator must immediately notify the sponsor (or designee).

Serious AEs that occur more than 30 days after the last dose of IMP need not be reported unless the investigator considers them related to the IMP.

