9.4.1. Assessment of AEs

At every study visit, participants will be asked a standard non-leading question to elicit any medically related changes in their well-being. They will also be asked if they have used any new medications, changed concomitant medication regimens (prescription or OTC medications), or had unplanned visits to their general practitioner since the last visit.

In addition to participant observations, AEs identified from any study data (e.g., laboratory values, physical examination findings, ECG changes) or identified from review of other documents (e.g., participant diaries) that are relevant to participant safety and considered clinically significant will be documented on the AE page in the CRF.

If the participant reports an adverse event, the following will be recorded in the source and on the eCRF:

1. Description of the event
2. Date and time of onset and resolution (duration)
3. CTCAE v5.0 grade (Grade 1 – 5)
4. Seriousness (does the event meet the above definition for an SAE)
5. Causality, relation to investigational product
6. Action taken regarding investigational product
7. Outcome
8. If any Concomitant Medications were given due to the AE
9. Whether the AE resulted in participant withdrawal from the study
10. Investigator-specified assessment if the AE is related to a recent/current COVID infection
11. If a COVID positive PCR test received within the last 14 days

Signs or symptoms of a participant's atopic dermatitis should be recorded as AEs only if their nature changes considerably or their frequency or intensity increases in a clinically significant manner as compared to the clinical profile known to the Investigator from the participant's history.

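### The cluster halting rule in protocol 9.9 names grade 3 AEs without 'or above', so a same-type cluster first recorded at grade 4 or 5 can escape the mandatory halt, mainly when the events are SAEs rated only possibly related

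*Protocol*

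**What the plan says.** Protocol 9.9 lists three events, any one of which halts the study:

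1. "One or more SAE considered definitely or probably related to the investigational product".
2. "Three or more participants with grade 3 AEs of the same type considered definitely, probably, or possibly related to the investigational product".
3. A documented *Prevotella histicola* infection in a sterile space. This is not tied to grade and plays no part below.

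Section 9.4.1 has each AE graded from 1 to 5 under CTCAE v5.0 and has seriousness recorded as a separate item. Section 9.4.2 asks for changes in severity to be documented, so that the time spent at each intensity can be assessed.

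Where the documents mean a grade and everything worse, they say so. The primary safety categories in protocol 3.1.1 include "TEAEs of Grade 3 or above". Protocol 11.3.1 and SAP 9.2 use the same form, and SAP 11.7.1 and 11.7.2 use it for the QTcF and vital-sign flags. Nothing in either document extends the second criterion of 9.9 to grades 4 and 5. The SAP's early-stopping sections only settle which outputs are produced.

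**The concern.** A halting rule is meant to take discretion away once a set threshold is crossed. Followed to the letter, this one stops the study for three possibly related grade 3 events of one type but does not have to stop it for three possibly related grade 4 events, or deaths, of that type. The SAE criterion does not repair this, because it leaves out the 'possible' category that the cluster criterion includes. The protocol itself treats a possible relationship as study-drug related (3.1.1, 11.3.1), and 9.4.3 defines it as one where the product may have contributed. At stake is whether a more severe cluster forces a halt or is left to judgment.

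**Working it through.** The plan gives no operating characteristic for the halting rule, so there is no figure to reproduce. The check applies criteria 1 and 2 to a same-type cluster in three participants.

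**Inputs**
- Criterion 1: at least 1 SAE, relationship probable or definite (9.9).
- Criterion 2: at least 3 participants, same type, grade 3, relationship possible, probable or definite (9.9).
- Seriousness: the criteria in 9.3.
- Assumption: grade 5 is fatal and therefore always serious under 9.3.

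**Result for three participants**

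| Grade on record | Serious | Relationship | Criterion 1 | Criterion 2 as written | Criterion 2 with 'or above' |
|---|---|---|---|---|---|
| 3 | Yes or no | Possible, probable or definite | Only if serious and probable or definite | Halt | Halt |
| 4 or 5 | Yes | Probable or definite | Halt (one event is enough) | No | Halt |
| 4 or 5 | Yes | Possible | No | No | Halt |
| 4 | No | Possible, probable or definite | No | No | Halt |
| 3, then 4 or 5 | Yes | Possible | No | Arguable | Halt |

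Rows three and four are the gap. Running the same rules with 50 participants instead of three changes nothing in those rows, because neither criterion has another count that a larger cluster could reach.

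**Main case (row three).** It does not depend on how seriousness is judged: the events are already SAEs, and only the causality rating keeps them out of criterion 1.

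**Rarer case (row four).** It needs a related grade 4 AE that is not serious. That is possible, because grade and seriousness are separate fields and the life-threatening criterion requires that the event "Is life-threatening that is, poses an immediate risk of death as the event occurred", with hypothetical risk expressly excluded. It is narrow for two reasons. Section 9.3 also makes an AE serious if it "Is an important medical event that, based upon appropriate medical judgment, may jeopardize the participant". And 9.10 records a laboratory abnormality as an AE only when the investigator judges it clinically significant, which filters the likeliest source of non-serious grade 4 events.

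**Path of the grade (row five).** Because 9.4.2 has severity changes documented, an AE that stood at grade 3 before worsening has a grade 3 record and could be counted. The same argument could be made for one that passes through grade 3 while improving. Section 9.9 does not say which recorded grade applies. The gap is therefore clear only for AEs with no grade 3 record, the plain example being an event first recorded at grade 4 or 5.

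**The case against.** The strongest reply is that any safety physician would read grade 3 here as a floor, and that the oversight around SAEs makes an unnoticed cluster implausible. Much of this stands. SAEs go to the Medical Monitor and sponsor within 24 hours (9.5) and are under ongoing review (9.8). Section 9.4 adds that "The Medical Monitor shall promptly review all information relevant to the safety of the investigational product". An individual participant stops treatment when the investigator judges that a serious AE requires it (5.4), and the sponsor may suspend the study at any time (10.4). These provisions make escalation likely. None of them obliges a halt, which is what 9.9 is for.

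The amendment log says the halting language was revised on FDA recommendation. It does not show what was recommended, so it neither supports nor undermines the omission.

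Two stronger readings are tempting. A reader might infer that grade 4 and 5 clusters can never trigger criterion 1 or 2, whatever their size. The documents do not support that: criterion 1 catches any SAE rated probable or definite, and an AE with a grade 3 record may count under criterion 2. A reader might also tally the uncovered combinations of grade, seriousness and causality as a measure of the gap. Such a tally fixes one grade per AE, contrary to 9.4.2, and weights very unlikely combinations equally with likely ones, so it says nothing about risk.

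**Conclusion.** The point holds as a minor wording fault. On the literal text, a mandatory halt applies to a same-type cluster at grade 3 but not to one first recorded at grade 4 or 5 when the events are SAEs rated possibly related or, more rarely, related grade 4 AEs that meet no SAE criterion.

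A reader might infer that the sponsor meant to exempt the worse events. The documents do not support that; the consistent use of 'or above' elsewhere points to an omission.

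The size cannot be put as a probability, since no event rates are given. SAP section 14 records that the study was terminated early after the parent study missed its primary endpoint, so the practical effect here is probably small. The Protocol Summary allows for use as an extension to future studies, but only as a possibility, and the current text names EDP1815-207 alone as parent. The conclusion rests on reading 9.9 literally and on taking grade 5 as fatal.

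**What to change.** In the second criterion of protocol 9.9, insert 'or above' directly after 'grade 3'. Leave the three-participant threshold, the same-type condition and the causality levels as the sponsor set them.

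No further clause on which grade to count is needed. With the floor in place, an AE that reached grade 3 or worse at any time qualifies whether it is counted at its peak or at any recorded grade.

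The cost is two words in a protocol amendment with a note to sites, and a slightly higher chance of a halt. The added halts would be for clusters more severe than those that already stop the study. As this study ended early, the change matters mainly if the wording is used again.

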9.10. Laboratory Measurements

Standard laboratory analyses to understand safety and tolerability include the following measurements:

Hematology	Biochemistry	Urinalysis
Complete Blood Count with differentials:	Alanine Aminotransferase (ALT)	Bilirubin
Hemoglobin	Aspartate Aminotransferase (AST)	Blood
Hematocrit	Creatinine	Glucose
Platelet count	C-Reactive Protein (CRP)	Ketones
Red blood count (with percent reticulocytes)	Gamma-glutamyl transpeptidase (GGT)	Nitrites
Mean Corpuscular Hemoglobin (MCH)	Potassium	pH
Mean Corpuscular Hemoglobin Concentration (MCHC)	Sodium	Protein
Mean Corpuscular Volume (MCV)	Total Bilirubin	Specific Gravity
White blood cell count:	Urea	
Basophils		
Eosinophils		
Lymphocytes		
Monocytes		
Neutrophils		

For WOCBP, urine pregnancy testing will be conducted at each study visit.

Additional testing may be ordered if needed, to further assess an adverse event (AE), or if there is any suspicion that a participant may be pregnant, throughout the course of the study.

Only abnormal laboratory test results (hematology, clinical biochemistry, or urinalysis) or other safety assessments (e.g., ECGs, vital sign measurements), which are clinically significant in the medical and scientific judgment of the investigator, are to be recorded as AEs or SAEs.

A central laboratory will be used for all laboratory analyses. Details of sample collection and handling procedures will be provided in the specific laboratory manual.

